#### 5) Resources available to conduct the Human Research

- The naturopathic medical program currently has 77 students, so we are aiming for a high participation rate from the students.
- Recruitment will take place from May 2019 until August 2019. We expect the research activity to take place during the Fall 2019 semester.
- The UB Naturopathic Clinic has 19 treatment rooms and 1 large classroom which provides ample space for the research to occur.
- We have one pulse-oximetry device for calculating heart rate
- We have five sphygmomanometers for performing manual blood pressure readings
- We need one 4oz. bottle of *Passiflora incarnata* solid extract by Wise Woman Herbals, which has been donated by the company.
- The co-investigators are:

UB HRP-503 TEMPLATE: Protocol

PROTOCOL TITLE: Investigating the short-term effects of *Passiflora incarnata* and mobile audio-guided meditation on blood pressure and heart rate in naturopathic medical students

PROTOCOL DATE: 3/28/19

Template Revised: June 14, 2010

- [name], ND has been associated with the UB Naturopathic Clinic for 3 years as a supervising physician. She has full knowledge of UB Naturopathic Clinic culture and policies.
  - [name], MD who has vast research experience both at UBSNM and at Yale.
  - [name] – Student Research Assistant, current first year ND student, has research and biology experience from Stonybrook University
  - [name] – Student Research Assistant, current second year ND student– has research experience from Eastern Connecticut State University
  - [name] – Student Research Assistant, current second year ND student– has research experience at the University of Bridgeport School of Naturopathic Medicine in the Anatomy Lab with [name]
- In the event of an adverse reaction to the *Passiflora incarnata* extract or the meditation, Student Health Services is available on the first floor of the Health Sciences Building
  - The research team will meet and have a training session before the research session occurs
  - All research team members are CITI-certified

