**d) Procedures involved in the Human Research\***

i) This will be a randomized, double-blind, placebo controlled trial.

ii) Students will be randomized to Group I, II, or III before the study begins

UB HRP-503 TEMPLATE: Protocol

PROTOCOL TITLE: Investigating the short-term effects of *Passiflora incarnata* and mobile audio-guided meditation on blood pressure and heart rate in naturopathic medical students

PROTOCOL DATE: 3/28/19

Template Revised: June 14, 2010

- iii) Naturopathic medical students will come to the study area in groups of 15-25 (each naturopathic cohort will be studied on a different day)
- iv) Naturopathic medical students will be studied on the day of a classroom examination with three left arm seated blood pressure readings and one heart rate reading taken 15 minutes after the end of the exam and then 15 minutes after that.
- v) All participants will be instructed to download Headspace app onto their smartphone prior to the research date
- vi) The participants will be randomized into three groups
  - (1) Group I
    - (a) Baseline (15 minutes post-exam) blood pressure readings (three left arm seated readings, average will be calculated) and one heart rate reading taken after at least 5 minutes of rest time without talking, eating, or caffeine consumption.
    - (b) This group will not be given any intervention. Subjects will sit quietly for 15 minutes and can read a book, surf the internet, etc. Subjects may not consume caffeine, eat food, or listen to any meditation during this time.
    - (c) Three left arm seated blood pressure readings and one heart rate will be taken 15 minutes after the baseline reading.
  - (2) Group II
    - (a) Baseline (15 minutes post-exam) blood pressure readings (three left arm seated readings, average will be calculated) and one heart rate reading taken after at least 5 minutes of rest time without talking, eating food, or caffeine consumption.
    - (b) 15 minutes after classroom examination – will be given 1/4 tsp of blackstrap molasses placebo and a 10 minute audio-guided mobile meditation session via the Headspace App. Subjects may not consume caffeine or eat food during this time.
    - (c) Three left arm seated blood pressure readings and one heart rate will be taken 15 minutes after the baseline reading.
  - (3) Group III

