  - (d) We are attempting to minimize adverse events by excluding participants who recently consumed cold medicine, cough suppressants, decongestant medication, antihistamine medication, stimulant medication, or tyramine containing foods to avoid interaction with *Passiflora incarnata*.
- (5) Initial data collected from the subjects
  - (a) The inclusion/exclusion criteria data will be collected from the participants before the start of the research (*see Attachment B*). This data will be collected in private with [name] or [name].
  - (b) Age, sex, significant past medical history (previous diagnoses), and medication usage. This information will be gathered via questionnaire (*see Attachment D*) before the start of the research. This data will be collected in private with [name] or [name].
  - (c) Adverse event survey will be collected from the participants by the end of the research day (*see Attachment C*)

e) **Data management\***

- i) Participants will be assigned a de-identifying code upon participation in the research
- ii) This code will be used to randomize the participants into Group I, II, and III
- iii) This code will be placed on both their initial questionnaire, inclusion/exclusion checklist, BP and HR readings, and their adverse events survey

UB HRP-503 TEMPLATE: Protocol

PROTOCOL TITLE: Investigating the short-term effects of *Passiflora incarnata* and mobile audio-guided meditation on blood pressure and heart rate in naturopathic medical students

PROTOCOL DATE: 3/28/19

Template Revised: June 14, 2010

- iv) This code will be linked with the participants' baseline and 15-minute blood pressure readings
  - v) A master sheet linking the code back to the subject's name will be stored on the password-protected University laptop belonging to only the co-investigators in a password-protected Excel sheet.
    - (1) This master sheet will not be printed or emailed between investigators.
  - vi) Hard copies of the inclusion/exclusion criteria checklist, the initial data questionnaire, BP and HR readings, and the adverse event survey will be stored in a locked file cabinet in the primary investigator's office. These forms will be shredded after three years.
  - vii) Power analysis – 45-60 subjects are needed to obtain 80%-90% power, respectively
  - viii) Data analysis will be done by our student research assistants and [name]
- f) Provisions to monitor the data for the safety of subjects\***

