- i) [name] will evaluate the adverse events survey and follow up with any participant who experience a moderate-severe adverse event
  - ii) Participants will be encouraged to report additional adverse events to [name] directly in the days following the research even once the survey has been handed in.
- g) Withdrawal of subjects\***
- i) Participants can voluntarily withdraw at any time
  - ii) Once a participant has withdrawn from the research, his/her data will not be included in our analysis
  - iii) Withdrawal may occur without the participants' consent if:
    - (1) His/Her smartphone or Headspace application is not functioning within 30 minutes after the end of his/her classroom examination
    - (2) He/She did not take the classroom examination that day
    - (3) He/She eats food/tyramine containing food, stimulant medication, alcoholic beverages, cold medicine, decongestant medication, antihistamine medication, cough suppressant medication, stimulant energy drinks, or consume caffeine within 2 hours before the study period or during the study period.
- 7) Risks to subjects\***
- a) Privacy Risks**
- i) Since naturopathic medical students will be studied in groups in one large room, the subjects will be informed that his/her classmates in the same room will know that he/she is participating in the study.
  - b) To minimize any privacy risks, all medical information will be collected in private before the day of the study. On the day of the study, we will not read the participants' blood pressure and heart rate readings out loud. We also will ask the participant to write down what medications or drinks taken on the day of the study

UB HRP-503 TEMPLATE: Protocol

PROTOCOL TITLE: Investigating the short-term effects of *Passiflora incarnata* and mobile audio-guided meditation on blood pressure and heart rate in naturopathic medical students

PROTOCOL DATE: 3/28/19

Template Revised: June 14, 2010

so that the participant does not have to say this information out loud in order to protect privacy.

- c) **Inconveniences: Time Invested/Timing with Classroom Examination**
  - i) The participants may be inconvenienced by sparing 45 minutes after his/her classroom examination
  - ii) The participant may feel distracted during his/her examination in anticipation of the research taking place after the examination
    - (1) This is unlikely, as the research is intended to have a relaxing benefit on the participant

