## 9) Provisions to protect the privacy interests of subjects

- a) Initial data to be gathered only by [name] or [name] include information regarding age, sex, past medical history (i.e. previous medical diagnoses), and medication usage (*See Attachment D*). This information will be linked to the

UB HRP-503 TEMPLATE: Protocol

PROTOCOL TITLE: Investigating the short-term effects of *Passiflora incarnata* and mobile audio-guided meditation on blood pressure and heart rate in naturopathic medical students

PROTOCOL DATE: 3/28/19

Template Revised: June 14, 2010

- participants' de-identified code. The code will only be linked back to the patient's name on a password-protected Excel sheet on the password-protected University computer belonging to the investigators.
- b) Blood pressure and heart rate readings will be linked to the participants' de-identified code. The code will only be linked back to the patient's name on a password-protected Excel sheet on the password-protected University computer belonging to the investigators.
  - c) The adverse event survey (*see Attachment C*) will be linked to the participants' de-identified code. The code will only be linked back to the patient's name on a password-protected Excel sheet on the password-protected University computer belonging to the investigators.
  - d) Only [name] and [name] will have access to the participants' data. The student RAs will not have access to the subject's data with the exception of their blood pressure and heart rate readings, as the student RAs will be collecting these measurements.
  - e) Being that the participants are students, they will be assured that their data will be kept completely confidential and stored only on password-protected excel sheets and password-protected computers. They will be assured that their questionnaire answers will not be used for any other academic means other than the intended research. They will be assured that the inclusion/exclusion criteria checklist, initial data questionnaire, and adverse events questionnaire will not be accessible by the student RAs. They will be assured that their willingness to participate in the research will in no way affect the way that they are treated in the classroom by their professors. They will be assured that choosing to participate or not to participate in the research will not affect their grade in their naturopathic classes. There will be no extra credit given for participating in the research.

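### With all three groups in one large room, nothing keeps the student assistants who read blood pressure manually from seeing who is in Group I before the second readings

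*Protocol*

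**What the plan says.** Protocol section 6(d)(i) sets the standard: "This will be a randomized, double-blind, placebo controlled trial". Section 6(d)(iii) brings a whole cohort to each session: "Naturopathic medical students will come to the study area in groups of 15-25 (each naturopathic cohort will be studied on a different day". Section 6(e)(ii) makes the individual the unit of allocation: "This code will be used to randomize the participants into Group I, II, and III". Sections 7(a)(i) and 9(f) place the session: "Since naturopathic medical students will be studied in groups in one large room".

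Under section 6(d)(vi), what an onlooker would see differs between groups. Of Group I it says: "This group will not be given any intervention". Those participants sit quietly and may read or use the internet. Group II "will be given 1/4 tsp of blackstrap molasses placebo and a 10 minute audio-guided mobile meditation session via the Headspace App". Group III takes the extract mixed into molasses and does the same meditation. In every group the second readings follow 15 minutes after baseline.

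Section 9(d) gives the student assistants access to blood pressure and heart rate data, "as the student RAs will be collecting these measurements". Section 5 lists five sphygmomanometers for manual readings, one pulse oximeter for heart rate and three student assistants. On space it says: "The UB Naturopathic Clinic has 19 treatment rooms and 1 large classroom which provides ample space for the research to occur". Section 6(c) makes both blood pressure and heart rate primary endpoints.

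**The concern.** A manual cuff reading depends on the person who takes it. If that person knows who has just meditated and who has merely sat, expectation can move the recorded value. Section 2 states the expected direction, a fall, so any such shift would tend to favour the hypothesis.

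The contrasts at stake are I versus II and I versus III. They are the only ones that can show an effect of meditation or of the combination. The molasses placebo masks II against III and does nothing for Group I.

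This is a matter of study conduct, so no statistical analysis plan can repair it. A bias already in the recorded value cannot be removed later. Averaging three readings does not help if all three are taken by the same informed assessor.

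**Working it through.** **1. Can the assessors see the difference?** Set side by side, the sections give this chain.

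- Individual randomization within cohorts of 15 to 25 means that the groups are mixed in each session (6(d)(iii), 6(e)(ii)).
- All participants of a session are in one room (7(a)(i), 9(f)).
- The assistants are needed at both ends of a 15-minute interval, and the intervention lies inside it (6(d)(vi), 9(d)).
- No section mentions a screen, a separate place for the intervention, or a rule about where the assistants are meanwhile.

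The spoonful is the clear marker of Groups II and III. Phones and headphones are a weaker one, because Group I may use the internet. Groups II and III look alike to an onlooker, so II versus III is untouched by this route.

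**2. Would it be enough for the assistants to leave between sets?** One set for a session is 15 × 3 = 45 to 25 × 3 = 75 cuff readings. At an assumed 1 minute each, three assistants need 45/3 = 15 to 75/3 = 25 minutes. The gap between a participant's two sets is 15 minutes. The sets can therefore overlap, and there may be no common interval in which the assistants could be absent.

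**3. Are there enough rooms?** The protocol lists 19 treatment rooms for 15 to 25 participants. If every participant spends the interval in a separate room, at most 25 − 19 = 6 need an overflow area.

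**4. What might the bias do?** The protocol gives no SD and no figure for assessor shift, so everything here is assumed: n = 20 per group, SD of the 15-minute change 6, 8 or 10 mmHg, true effect zero, and an unadjusted two-sided 5% two-sample t-test. The shift is a difference in group means, after averaging each participant's readings.

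- Standard error: SE = SD × √(2/n). For SD 8: 8 × √(2/20) = 2.530 mmHg.
- Noncentrality: shift / SE. For 1, 2, 3 mmHg at SD 8: 0.395, 0.791, 1.186.
- Degrees of freedom: 2n − 2 = 38; critical value 2.024.
- False-positive rate: the probability that a noncentral t falls beyond ±2.024.

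| SD of change (mmHg) | no shift | 1 mmHg | 2 mmHg | 3 mmHg |
|---|---|---|---|---|
| 6 | 0.050 | 0.081 | 0.177 | 0.338 |
| 8 | 0.050 | 0.067 | 0.120 | 0.212 |
| 10 | 0.050 | 0.061 | 0.095 | 0.152 |

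More participants make it worse, because a fixed bias is measured against a smaller standard error. With 23 per group (about 70 in total) and SD 8 the rates are 0.070, 0.132 and 0.238.

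**The case against.** **Presence during dosing is not stated.** A reader might infer that the assistants watch the dosing and therefore know each participant's group. The documents do not support that. They say neither where the assistants are between reading sets nor who hands out the spoonfuls. The one-room sentence appears in a privacy notice, not in the measurement procedure, and section 5 offers the treatment rooms as study space too. An assistant busy with one cuff may also miss another participant's spoonful. This stands, and it limits the claim to what assessors may see. It does not remove the claim: the plan as written allows the view and contains nothing to prevent it.

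**The size is assumed.** No section supports a particular shift in mmHg, and the largest figure in the table combines the largest shift with the smallest SD. This stands too. The table is not an estimate of this trial's error rate.

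**The scope is limited.** One might infer that every primary comparison is compromised. It is not. Heart rate comes from a pulse oximeter, and II versus III, the contrast that isolates the extract, is masked from the assessors.

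**Any remedy is partial.** Group I participants know that they received nothing, so their own expectations remain in both contrasts. This is true, but it is no reason to leave an avoidable assessor bias in place.

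**Conclusion.** The point holds in a limited form. As written, the plan leaves manual blood pressure in I versus II and I versus III open to assessor bias in the hypothesised direction, because nothing prevents the assistants from learning who is in Group I before the second readings. That they do learn it is a reasonable inference from the layout and timing, not a stated fact.

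Across the assumed shifts of 1 to 3 mmHg and SDs of 6 to 10 mmHg, the nominal 5% becomes about 6% to 34%. A mean shift of 1 mmHg matters little (6% to 8%); one of 3 mmHg matters a good deal (15% to 34%). The protocol should be changed before the first session, because the remedy is cheap and nothing can be done afterwards.

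**What to change.** Amend sections 6(d)(iii) to (vi), 7(a) and 9(f) so that the intervention and the measurements take place apart, and reconcile those sections with the space listed in section 5.

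- All participants, Group I included, spend the interval out of the assistants' sight in the treatment rooms, with a screened area for any overflow. The faculty investigators hand out the spoonfuls there.
- The assistants stay at a fixed measuring station with the cuffs and the one oximeter. Participants come to it in staggered order and sit at rest before the readings, in the same way in every group.
- Phones, headphones and spoons stay behind, and participants are told not to reveal their group.
- The second set is written on a new sheet that carries only the code, with no group and no baseline values.
- The plan should not rely on the assistants leaving the room between sets, since the sets may overlap.

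The cost is a room plan, staggered timing and a second sheet. The number of readings does not change, and no participants or staff are added. Timing needs a trial run: after a 10-minute meditation, 15 − 10 = 5 minutes remain for taking the spoonful, walking to the station and sitting at rest, and the faculty investigators have several rooms to cover. The change removes assessor bias only; Group I participants remain unblinded, and the protocol should say so.

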anxiety (12-14) with mild and non-serious adverse effects, including headache, abdominal pain, and flatulence. Doses in these trials ranged from 260mg – 700mg. Rare side effects from chronic *Passiflora* use included vasculitis, asthma, rhinitis, and urticaria (15). One case study from 2000 revealed a toxic reaction to *Passiflora incarnata*, in which the patient experienced various cardiovascular effects, including ventricular tachycardia (16). Passionflower extract also contains harmine and hardline which may stimulate uterine contractions, and is therefore contraindicated in pregnancy. It has theoretical action as a platelet inhibitor, so it is contraindicated before surgery. A 2017 trial comparing *Passiflora incarnata* to midazolam before dental extraction found that both *Passiflora* and midazolam improved patients pre-procedure anxiety levels, and they concluded that the *Passiflora* was safe and effective in this one-time dosage (17). 50% of the participants in this trial experienced drowsiness as a side effect of the 260mg preoperative dosage. 20% experienced muscle relaxation, 5% experienced dizziness, 2.5% experienced an allergy, and 2.5% experienced epistaxis. A 2013 study evaluated the effects of 500mg *Passiflora incarnata* on anxiety levels before periodontal treatment. This study found significant reductions in anxiety in those taking the botanical extract with no reports of any adverse effects (18). Lastly, a 2001 study on 36 patients found comparative anxiolytic effects between *Passiflora* and oxazepam with mild-moderate dizziness, drowsiness, impairment of job performance, and confusion listed as the most frequent side effects for both interventions. In the *Passiflora* group, two participants experienced a mild-moderate allergic reaction and two participants experienced mild-moderate ataxia (19). There is no evidence in the current literature that *Passiflora* is an abortifacient or teratogen. To our knowledge, no recent human trials have been done to investigate the effects of *Passiflora incarnata* on blood pressure. A related plant, *Passiflora edulis* has demonstrated antihypertensive properties in rats (20, 21).

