## 6) Study Design

### a) Recruitment Methods

- i) We will recruit from the naturopathic medical program, which currently has 77 enrolled students.
- ii) A flyer will be posted and emailed out to the naturopathic student body (*see Attachment A*)
- iii) Naturopathic student participants will NOT be recruited during class time with [name] or [name] to reduce any conflict of interest or feeling of persuasion that the student may have.
- iv) All naturopathic students will be invited to participate. Once a student expresses interest, he/she will be given the inclusion/exclusion criteria checklist (*see Attachment B*) to ensure eligibility.
  - (1) Exclusion criteria: Those taking hypertensive, blood-thinning, or anti-anxiety medications (including MAOI medications), those with surgery in the past 2 weeks or coming in the next 2 weeks, those females who are currently pregnant or could be pregnant
    - (a) “Day Of” exclusion criteria: consuming food, caffeine, use of stimulant medication, use of MAOI medication, alcoholic beverages, consumption of tyramine containing foods (i.e. blue cheese, gorgonzola cheese, red wine, cured meat, cured fish, sauerkraut, sourdough bread, soy sauce, teriyaki sauce, miso tempeh, or overripe fruits), consumption of cold medicine, antihistamine medication,

UB HRP-503 TEMPLATE: Protocol

PROTOCOL TITLE: Investigating the short-term effects of *Passiflora incarnata* and mobile audio-guided meditation on blood pressure and heart rate in naturopathic medical students

PROTOCOL DATE: 3/28/19

Template Revised: June 14, 2010

decongestant medication, cough suppressant medication, or use of stimulant energy drinks within 2 hours before the study period.

(2) Participants will not be given any incentive to participate (i.e. no payment or “extra credit” will be given).

v) Interested participants will be screened for eligibility (see Attachment B) and allowed to participate if they do not meet any of the exclusion criteria

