  - f) Since naturopathic medical students will be studied in groups in one large room, the subjects will be informed that his/her classmates in the same room will know that he/she is participating in the study. To minimize any privacy risks, all medical information will be collected in private before the day of the study. On the day of the study, we will not read the participants' blood pressure and heart rate readings out loud. We also will ask the participant to write down what medications or drinks taken on the day of the study so that the participant does not have to say this information out loud in order to protect privacy.

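### Pregnancy and surgery status are asked before the study day and not asked again before dosing, although the protocol calls the extract contraindicated in both (cheap safety improvement, minor)

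*Protocol*

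**What the plan says.** Section 3 (Background) says the extract "may stimulate uterine contractions, and is therefore contraindicated in pregnancy". On surgery it says: "It has theoretical action as a platelet inhibitor, so it is contraindicated before surgery". Section 6(b)ii accordingly excludes anyone who is or could be pregnant, and anyone with surgery within two weeks either side of the research date. Section 6(d)vii(4)(c) relies on the pregnancy exclusion to limit adverse events.

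On timing, section 6(a)iv says: "Once a student expresses interest, he/she will be given the inclusion/exclusion criteria checklist". Section 13 has consent follow within days of the student being told of eligibility, on a separate day ahead of the research. Section 7(b) says that "all medical information will be collected in private before the day of the study", and 9(f) carries the same privacy sentence: "To minimize any privacy risks, all medical information will be collected in private before the day of the study". Section 5 gives the calendar: "Recruitment will take place from May 2019 until August 2019. We expect the research activity to take place during the Fall 2019 semester".

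For the study day itself, the list in 6(a)iv(1)(a) begins with "consuming food, caffeine, use of stimulant medication, use of MAOI medication, alcoholic beverages" and continues with foods, drinks and medicines. Criterion 6(b)ii(9) covers intake in the preceding two hours. Sections 7(b) and 9(f) have participants note in writing which drugs and drinks they have had that day.

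**The concern.** An exclusion protects a participant only if the excluded state is known when the dose is given. Here the two states that the protocol calls contraindications are asked about at screening, and no described step asks about them again. A Group III participant who becomes pregnant, or has an operation newly arranged, between screening and the session would pass through the written procedure and receive the extract without being asked. The shorter-lived matters (caffeine, tyramine-containing foods, cold remedies) are checked on the day. The stake is the safety of a few healthy volunteers who are also the investigators' students. The endpoints, sample size and analysis are not involved.

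**Working it through.** There is no planned figure to reproduce. The check sets the sections side by side and adds a few counts.

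**1. Conditions and study-day steps**

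| Study-day step in the text | Covers | Pregnancy? | Surgery? |
|---|---|---|---|
| Day-of list, 6(a)iv(1)(a) | food, drink, medication (MAOIs included) | no | no |
| Criterion 6(b)ii(9) | intake in the last 2 hours | no | no |
| Written note, 7(b) and 9(f) | drugs and drinks that day | no | no |
| Withdrawal grounds, 6(g)iii | app failure, missed exam, intake | no | no |
| Group III procedure, 6(d)vi(3) | baseline readings, then dose | no | no |

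Stated contraindications: 2. With a described study-day question: 0. Grounds in 6(g)iii: 3. Naming either condition: 0.

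**2. Interval between screening and dosing**

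Eligibility comes before consent (13(a), 13(c)), and consent is on an earlier day than the research (13(a)). The minimum is therefore 1 day. No maximum is stated. Session dates are not given. Only as an illustration, if the Fall semester is assumed to run from September to December, the gap could be anything from days (late August to early September) to about 7 months (May to December). Neither 6(b)iii nor 6(d)vii(5)(a) fixes a screening date, so the documents do not establish where in that range a participant would fall.

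**3. What the existing criteria already catch**

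Section 6(b)ii(6)–(7) ties surgery to the research date, so an operation foreseeable at screening is caught. Section 6(a)iv words the same criterion as "those with surgery in the past 2 weeks or coming in the next 2 weeks", with no anchor date. Section 6(b)ii(5) excludes possible as well as known pregnancy. What remains is a change after screening.

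**4. People exposed**

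Assuming equal allocation to three groups: 45/3 = 15 and 70/3 ≈ 23 would receive the extract. The documents give no rate at which status would change, so no expected count can be offered.

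**5. Room in the schedule**

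Sessions hold 15 to 25 students. Shared between two investigators, that is 15/2 ≈ 8 to 25/2 ≈ 13 notes each. At an assumed 0.5 to 1 minute per note, reading takes 8 × 0.5 = 4 to 13 × 1 = 13 minutes. Baseline is 15 minutes after the exam and its last 5 minutes are silent rest, so 15 − 5 = 10 minutes are free for writing. Reading can continue while participants rest.

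**The case against.** The strongest reply is that nothing here is stated wrongly. The timing sentence is a privacy provision, and *medical information* in it may mean only the history questionnaire (Attachment D). For the eligibility checklist (Attachment B), 6(d)vii(5)(a) says only that it is collected before the research starts. Attachment B and the consent form are not shown and may ask participants to report changes. The criteria are broad, and participants may withdraw at any time. Asking about pregnancy on the study day, with classmates in the same room and instructors reading the answers, has a privacy cost that the protocol deliberately avoids.

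Much of this stands, and it rules out several readings that a reader might infer:

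- *All eligibility is closed before the study day.* It is not: 6(b)ii(9) can be answered only on the day.
- *Medication is not rechecked.* The written note does this in large part, so re-asking every excluded drug would mostly duplicate it.
- *The protocol permits dosing someone known to be pregnant.* It does not: that would breach 6(b)ii and 15(d).
- *Months pass between screening and dosing.* The calendar in section 5 allows this, but no screening or session date is given.
- *Section 14(b) shows that the protocol rechecks status after a week.* That repeat conversation concerns recall of the consent details before signing, not eligibility.

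What survives is narrower. As written, the text places medical questions before the study day and describes no later question on the two contraindications. If Attachment B does ask on the day, the sentence in 7(b) and 9(f) still needs an exception to agree with it.

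**Conclusion.** The point holds as a minor, cheap safety improvement. A change in pregnancy or surgery status after screening would not be picked up by any described step unless the participant volunteers it or Attachment B asks.

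The size is small: a single dose, one of three groups (about 15 to 23 people under equal allocation), a platelet action that section 3 calls theoretical, and that section's statement that the literature shows no abortifacient or teratogenic effect. The number of participants whose status would change is unknown. The conclusion rests on the protocol text alone and could be weakened by the content of Attachment B or the consent form. It gives no ground to doubt the endpoint, the sample size or the analysis.

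**What to change.** 1. Add two items to the private written study-day note: pregnant or could be pregnant since screening; and surgery in the past two weeks or planned in the next two. All participants in all three groups complete it after the exam and before baseline readings, so before anything is given. Only the two investigators read it, in line with the access limits in section 10(d).
2. Add a ground to 6(g)iii: the participant meets an exclusion criterion on the study day. Apply it before baseline readings and without regard to allocation.
3. In 7(b) and 9(f), add an exception to the timing sentence for this short written reconfirmation.
4. In 6(a)iv, anchor the surgery window to the research date, as 6(b)ii already does.

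No new criterion, test or staff is needed.

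**Cost.** A minute or two per participant, within the existing schedule. Because students are randomized before the study begins, a few may be excluded after randomization. They would have no readings, so the exclusions cannot depend on outcomes, and the target of 70 leaves 70 − 60 = 10 above the protocol's figure for 90% power and 70 − 45 = 25 above its figure for 80%. The privacy burden is small but real: a student sent away may be noticed by classmates, so the investigators should handle this discreetly and give no reason in the room.
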